During Part A, incidence of AEs was slightly higher in the nemolizumab groups than in the placebo group. AEs that occurred in 5% or more of nemolizumab-treated patients (all groups pooled) were (worsening of) dermatitis atopic, nasopharyngitis, upper respiratory tract infection, edema peripheral, and blood CPK increased. Dermatitis atopic, edema peripheral, and headache were observed more often in each of the nemolizumab groups compared to the placebo group, but with generally no evidence that the incidence increased with higher dose. There was an apparent dose relationship for edema peripheral in the nemolizumab Q4W groups; however, most of the cases occurred during part A, were transient, of mild or moderate intensity and none led to treatment discontinuation. Various AEs that could be grouped as “injection-related reactions (IRR)” or “skin infection” were also observed in a higher frequency with nemolizumab than with placebo. Severe AEs were reported more frequently in nemolizumab groups than in placebo group (in Part A), but there was no evidence that the incidence increased with higher dose. During the entire study (Part A and B), AEs that occurred in 5% or more of nemolizumab-treated patients (all groups pooled) were nasopharyngitis, dermatitis atopic, blood CPK increased, upper respiratory tract infection, headache, edema peripheral, and impetigo. The majority of AEs were mild or moderate in intensity. No clinically relevant findings were observed during the study for laboratory tests, vital signs, physical examination or electrocardiogram (ECG). Treatment-emergent antibodies to nemolizumab were observed in 7.1% of the patients in the pooled nemolizumab groups. In addition one patient in the 0.1 mg/kg Q4W group with anti-nemolizumab antibodies present from baseline developed neutralizing antibodies at 64 weeks.

Based on the safety data from these two completed studies, no risk of nemolizumab has been identified. Potential important risks to be monitored closely include injection-related reactions (IRR), asthma, exacerbation of AD, and skin infection; while peripheral edema and headache are considered as potential non-important risks.

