7.3 Pharmacokinetic and anti-drug antibody assessments

Blood sample will be collected according to [Table 2](#) to determine the PK profile of nemolizumab and to assess anti-nemolizumab antibodies (ADA). The serum concentration of nemolizumab will be assessed at baseline, weeks 1, 2, 4, 8, 12, 16, 20, 24, 28, 32 and at any unscheduled visit for safety reasons. ADA will be assessed at baseline, weeks 4, 8, 16, 24, 32 and at any unscheduled visit for safety reasons.

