9.1.5.4 PK parameters and ADA analyses

The PK parameters derived using non-compartmental techniques will be regarded as primary endpoints for the pharmacokinetic analyses (see details in Section 7.3.3). Primary inference for all the PK parameters will be based on the pharmacokinetic analysis population.

Descriptive statistics (n, arithmetic mean, standard deviation [SD], minimum, median, maximum) by treatment group will be calculated for all derived pharmacokinetic endpoints. Geometric means and between-subject coefficients of variation (CVb) will be calculated for log_e-transformed AUC_{0-28d}, C_{trough} and C_{max} where:

Following log_e-transformation, AUC_{0-28d}, C_{trough} and C_{max} will be analyzed separately using analysis of variance (ANOVA), fitting a model with treatment group as a fixed effect. The residual variance from the model will be used to calculate point estimates and 90% CIs for the least squares means for each treatment formulation on the log_e scale. These estimates will be back transformed to give point estimates and 90% CIs on the original scale.

The concentration at each time point will be summarized as arithmetic mean, standard deviation, median, minimum, and maximum, number of BLQs (Below the Limit of Quantification). PK parameters using geometric means will be compared to determine when steady state conditions are achieved during the treatment period.

The potential relationship between plasma concentrations of nemolizumab and change in EASI, pruritus NRS, biomarkers or other indicators of disease activity will be explored using PK/PD modeling, as appropriate.

Incidence of positive ADA results will be summarized by treatment group (absolute occurrence and percent of subjects). ADA results presentation will be detailed in the SAP.

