- AUC_{0-t} : Area under the concentration time curve calculated by the mixed linear logarithmic trapezoidal method from the last administration (week 20) up to the sampling time corresponding to the last quantifiable concentration (C_{last}).

- AUC_{0-inf} : Area under the plasma concentration time curve calculated by the mixed linear logarithmic trapezoidal method from the last administration (week 20) and extrapolated to time infinity
- $t_{1/2}$: the terminal half-life value ($t_{1/2}$) will be calculated using the equation $\ln 2/k$ after the last drug injection (week 20).

At weeks 4, 8, 12, 16, 20, 24, 28, 32:

- C_{trough} : The residual drug concentration (pre-dose level).
- Accumulation index: calculated with the serum nemolizumab trough concentration obtained 4 weeks after the first dose (week 4) and 4 weeks after last drug injection (week 24).

ADA will be evaluated using a validated ELISA screening assay. If serum circulating ADA is detected, they will be characterized using a validated assay. ADA assessment will include screening, confirmatory, titer, neutralizing antibodies (Nab) and IgE-based assays.

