 - AUC_{0-24w}
 - C_{trough} week 24

- Percent change in sleep disturbance NRS vs individual serum concentrations (scatter plots):
 - at Week 4
 - AUC_{0-28d}
 - C_{trough} week 4
 - at Week 12
 - AUC_{0-12w}
 - C_{trough} week 12
 - At week 24
 - AUC_{0-24w}
 - C_{trough} week 24
- Proportion of subjects achieving IGA success (defined as IGA 0 [Clear] or 1 [Almost Clear]) vs quartile of concentrations (bar plots):
 - at Week 12
 - AUC_{0-12w}
 - C_{trough} week 12
 - At week 24
 - AUC_{0-24w}
 - C_{trough} week 24
- EASI-75 response rate vs quartile of concentrations (bar plots):
 - at Week 12
 - AUC_{0-12w}
 - C_{trough} week 12
 - At week 24
 - AUC_{0-24w}
 - C_{trough} week 24
- Incidence of TEAEs in subjects treated with nemolizumab categorized by steady state trough serum concentration in 4 quartiles.

Incidence of positive ADA results will be summarized and plotted by treatment group (absolute occurrence and percent of subjects) at each visit. Incidence of treatment-related positive ADA (subjects who will become ADA positive only after Nemolizumab administration) will also be summarized and plotted by treatment group (absolute occurrence and percent of subjects) at each visit.

An interim PK and Exposure-Response analysis will be done with the bionalytical data available at Week 24 analysis (see Section 4.7.1.5). The interim analysis will include:

- Serum pharmacokinetic parameters will be listed by cohort, subject and day, and summarized by treatment.
- Serum Nemolizumab concentrations will be plotted by treatment group (individual PK profiles, mean PK profile)

- Descriptive statistics for calculated PK parameters will include: n, arithmetic mean, SD, median, minimum and maximum values.
- Geometric mean, geometric coefficient of variation (CVb), lower quartile (Q1), and upper quartile (Q3) will be presented for AUC_{0-28d} , AUC_{0-12w} , AUC_{0-24w} , AUC_{0-t} , C_{trough} and C_{max} . PK parameters will also be summarized by weight category. Analysis of PK parameters, AUC_{0-28d} , AUC_{0-12w} , AUC_{0-24w} , AUC_{0-t} , C_{trough} and C_{max} , using an analysis of variance (ANOVA) will be presented.
- The Exposure-Response analysis described above.
- Incidence of positive ADA results on individual PK profiles (plot with 3 different identifications for the negative ADA, for the treatment-related positive ADA and for the positive ADA).

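### The SAP's treatment-related ADA category has no treatment-boosted limb, and no titre or neutralizing-antibody summary is planned although both are measured

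*SAP*

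**What the plan says.** Protocol 9.1.5.4 hands the matter to the SAP: "ADA results presentation will be detailed in the SAP". SAP 4.9.1 then plans three ADA outputs.

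- **Overall incidence:** "Incidence of positive ADA results will be summarized and plotted by treatment group (absolute occurrence and percent of subjects) at each visit".
- **Treatment-related incidence**, also by group and visit, restricted to "subjects who will become ADA positive only after Nemolizumab administration".
- **ADA status on individual PK profiles**, listed among the outputs of the PK analysis at week 24: "plot with 3 different identifications for the negative ADA, for the treatment-related positive ADA and for the positive ADA".

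On measurement, SAP 3.2.4 states: "ADA assessment will include screening, confirmatory, titer, neutralizing antibodies (Nab) and IgE-based assays". On timing, Protocol 7.3 states: "ADA will be assessed at baseline, weeks 4, 8, 16, 24, 32 and at any unscheduled visit for safety reasons". Baseline status is therefore known, and titre and neutralizing activity are measured.

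For the phase 2a study, Protocol 1.2 reports: "Treatment-emergent antibodies to nemolizumab were observed in 7.1% of the patients in the pooled nemolizumab groups". It continues: "In addition one patient in the 0.1 mg/kg Q4W group with anti-nemolizumab antibodies present from baseline developed neutralizing antibodies at 64 weeks".

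**The concern.** Drug can provoke an antibody response in two ways. A subject who was negative may turn positive, or a subject who already had antibody may show a stronger response, or one of a different kind, after exposure. The SAP's treatment-related category captures only the first. It has no limb for the second, no rule for how large a titre rise would count, and no table of titre or neutralizing results.

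Safety and PK are the stated secondary objectives, and the trial is meant to support dose selection for later development. If some baseline-positive subjects respond to drug, the treatment-related incidence by arm will be too low. The PK plots, which exist partly to show whether antibody goes with altered exposure, will then give stable and rising responses the same label.

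The point also bears on a dose studied here. The phase 2a patient with pre-existing antibody was on 0.1 mg/kg every 4 weeks, and Protocol 3.4 equates this trial's 10 mg arm to about 0.13 mg/kg.

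**Working it through.** The plan states no ADA figure for this trial, so there is nothing to reproduce. The phase 2a rate of 7.1% cannot be reproduced either, because Protocol 1.2 gives neither its numerator nor its denominator. The check is mainly a reading of the definitions, followed by arithmetic for scale.

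**Step 1. Pass each kind of subject through the three planned outputs.** This assumes that a baseline-positive subject is still positive at the visit in question.

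| Subject | Overall incidence | Treatment-related incidence | PK plot label |
|---|---|---|---|
| A. Negative throughout | no | no | negative |
| B. Negative at baseline, positive later | yes | yes | treatment-related positive |
| C. Positive at baseline, titre unchanged | yes | no | positive |
| D. Positive at baseline, titre rises on drug | yes | no | positive |
| E. Positive at baseline, new neutralizing activity | yes | no | positive |

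Rows C, D and E are identical in every column, so no planned output separates them. The assays that would separate them (titre for D, neutralizing for E) are in SAP 3.2.4 but feed no described summary.

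**Step 2. Place the phase 2a patient.** With antibody from baseline and neutralizing activity later, this patient is row E. The protocol reports the patient in addition to the 7.1%. Under the present SAP definition, a similar patient here would again fall outside the treatment-related count.

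**Step 3. Scale.** Planned nemolizumab subjects: 3 × 50 = 150 (Protocol 5.1). Baseline ADA prevalence p is not in the documents, so 1%, 3% and 5% are assumptions. Expected number baseline-positive = 150 × p. Chance of at least one = 1 − (1 − p)^150.

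| Assumed p | Expected of 150 | Chance of at least one |
|---|---|---|
| 1% | 1.5 | 78% |
| 3% | 4.5 | 99% |
| 5% | 7.5 | more than 99.9% |

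For comparison, 7.1% of 150 is 0.071 × 150 = 10.65, or about 11 subjects with treatment-emergent antibody if the phase 2a rate recurred. The expected numbers in the table are ceilings on the expected undercount at each p, because they count everyone positive at baseline and not just those who respond. The true undercount could be zero.

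**The case against.** Several things can fairly be said for the plan.

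- **These subjects are not lost.** A reader might infer that baseline-positive subjects vanish from ADA reporting. They do not: they are in the overall incidence, and because a baseline sample is taken, pre-existing positivity can be seen. What is missing is narrower, namely the split between boosted and unchanged within that group.
- **The PK plots are not mislabelled.** A reader might infer that boosted subjects carry the wrong identifier. Under the SAP's own three labels, a baseline-positive subject is correctly marked positive, apart from the treatment-related ones, and the individual profile is still shown. The label is coarse, not wrong.
- **Phase 2a does not show boosting by drug.** A reader might take the protocol's account as an established pattern. It is one patient, with neutralizing antibodies at week 64, no reported titre rise and no attribution to drug. Here the last dose is at week 20 and planned sampling ends at week 32.
- **Other documents may cover it.** Protocol 7.3.1 refers to a bioanalytical plan and to a bioanalytical report appended to the study report. Titre and neutralizing results may appear there.
- **The consequence is small.** The ADA summaries are descriptive, and no test or primary endpoint depends on them.

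All of this limits how much can be claimed. It does not close the gap. The contents of the bioanalytical documents are not given, and the protocol assigns ADA presentation to the SAP. A results appendix does not replace a by-arm summary with its rule fixed in advance.

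**Conclusion.** The point holds as a minor gap in a descriptive safety and PK output. The treatment-related definition excludes every baseline-positive subject by rule, and no planned output shows whether such a subject's response changed on drug, although the assays to show it are being run.

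The size is unknown. It depends on baseline prevalence, which the documents do not give, and on the share of those subjects whose titre rises, which is also not given. The 1% to 5% range is assumed and gives a ceiling of about 1.5 to 7.5 of 150 subjects. It would be wrong to read the phase 2a report as an estimate of the undercount: it is a single patient, and whether that patient would meet a titre-based definition of boosting cannot be told from the protocol. The primary efficacy analysis is not touched.

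**What to change.** Before unblinding for the week 24 analysis, amend SAP 4.9.1 as follows.

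1. Tabulate by arm **treatment-induced** ADA (negative at baseline, positive later) and **treatment-boosted** ADA (positive at baseline, with a titre rise above a stated threshold). State the threshold in the SAP, or cite it from the bioanalytical plan if one is set there; the documents do not show whether it is.
2. Summarise neutralizing status by baseline ADA status in a separate row. Keep it apart from the titre-based category, since the one documented phase 2a case shows new neutralizing activity and no reported titre change.
3. Add a boosted identifier to the individual PK plots.

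The cost is one threshold to pre-specify, a few table rows and one more plot symbol. No new samples or assays are needed. Setting the rule while the trial is blinded avoids a classification chosen after the results are seen.

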4.9.2 Biomarker Analyses

Primary inference for all biomarker analyses (including, but not limited to, eosinophil TARC, IgE, IL6, IL8, and IL18) will be based on the observed cases. All biomarker variables (using logarithm transformation) will be summarized across treatments at each time point.

Any observations in trends within the Biomarker data may be explored with PK/PD correlations/models. All of this analysis will be considered exploratory. The outputs will be in a separate report.

The detailed analysis will be carried out by Biomarker group in GALDERMA, and will be reported separately.

4.9.3 Quality of Life and Productivity data Analyses

Primary study population for all QoL and productivity data analyses will be based on ITT population. The DLQI, HADS, EQ5D and productivity data will be summarized by treatment group and visit.

By-subject listings of these data should be provided.

4.9.3.1 Change from baseline in DLQI at each visit up to week 24

This endpoint will be analyzed as the primary efficacy endpoint using a MMRM approach.

In addition, the following analyses will be performed:

- A shift table (by visit) will be generated using the categories as described in Section 3.2.6.1.
- Change from baseline in each sub-scale (see Section 3.2.6.1) at each visit up to week 24 will be analyzed as the primary efficacy endpoint using a MMRM approach.

- Proportion of subjects achieving a change in DLQI score of at least 4 points at each visit up to week 24 will be analyzed using a CMH test as described in Section 4.7.3.1.

4.9.3.2 Change from baseline in HADS at each visit up to week 24

The following endpoints will be analyzed as the primary efficacy endpoint using a MMRM approach.

- Change from baseline in HADS anxiety sub-score at each visit up to week 24
- Change from baseline in HADS depression sub-score at each visit up to week 24

In addition, the following analyses will be performed using a CMH test as described in Section 4.7.3.1:

- Proportion of subjects with HADS anxiety sub-score ≥ 11 at each visit up to week 24
- Proportion of subjects with HADS depression sub-score ≥ 11 at each visit up to week 24

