7.5 Quality of life assessments

7.5.1 Dermatology Life Quality Index (DLQI)

DLQI is a validated 10-item questionnaire, covering domains including symptoms/feelings, daily activities, leisure, work/school, personal relationships and treatment (Finlay 1994, see APPENDIX 10). Subject will rate each question ranging from 0 (not at all) to 3 (very much), and the total score ranges from 0 to 30, with a higher score indicating a poorer QoL. DLQI will be administered according to the schedule of assessments only to the subset of subjects who fluently speak a language in which the questionnaire is presented (based on availability of validated translations in participating countries).

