3.2.6 Quality of life assessments

3.2.6.1 Dermatology Life Quality Index (DLQI)

DLQI is a validated 10-item questionnaire, covering domains including symptoms/feelings, daily activities, leisure, work/school, personal relationships and treatment. Subject will rate each question ranging from 0 (not at all) to 3 (very much), and the total score ranges from 0 to 30, with a higher score indicating a poorer quality of life (QoL). Please note that “Not relevant” is scored as 0, and Question 7, “prevented work or studying” is scored as 3. DLQI will be administered only to the subset of subjects who fluently speak a language in which the questionnaire is presented.

DLQI will be assessed at baseline, weeks 2, 12, 24, or early termination visit when applicable.

The DLQI score will be categorized as follows:

- 0-1 = no effect at all on subject’s life
- 2-5 = small effect on subject’s life
- 6-10 = moderate effect on subject’s life
- 11-20 = very large effect on subject’s life
- 21-30 = extremely large effect on subject’s life

The DLQI can be analyzed under 6 sub-scales, namely, symptoms and feelings (question 1 and 2), daily activities (question 3 and 4), leisure (question 5 and 6), work and school (question 7), personal relationships (question 8 and 9), and treatment (question 10).

For general inflammatory skin conditions a change in DLQI score of at least 4 points is considered clinically important.

Refer to Appendix 3 for details on scoring, data handling rules, and analysis on DLQI.

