4.2 General Presentation Considerations

Unless otherwise stated, descriptive summaries will be presented by treatment group. In all tables the treatment groups will be presented in the order of Placebo, Nemolizumab 10 mg, Nemolizumab 30 mg, and Nemolizumab 90 mg. Comparisons on the difference between each nemolizumab group and placebo will be presented.

Continuous data will be summarized in terms of the mean, standard deviation (SD), median, minimum, maximum, lower quartile (Q1), upper quartile (Q3), and number of observations, unless otherwise stated. Where data are collected over time, both the observed data and change from baseline will be summarized at each time point. The minimum and maximum will be reported to the same number of decimal places as the raw data recorded in the database. The mean, median, Q1, and Q3 will be reported to one more decimal place than the raw data recorded in the database. The SD will be reported to 2 more decimal places than the raw data recorded in the database. In general, the maximum number of decimal places reported shall be four for any summary statistic.

Categorical data will be summarized in terms of the number of subjects providing data at the relevant time point (n), frequency counts and percentages. Percentages will be presented to one decimal place. A percentage of 100% will be reported as 100%. Percentages will not be presented for zero counts. Percentages will be calculated using n as the denominator. If sample sizes are small, the data displays will show the percentages, but any textual report will describe

frequencies only. Changes from baseline in categorical data will be summarized using shift tables where appropriate.

P-values greater than or equal to 0.001, in general, will be presented to three decimal places. However, if a p-value is only presented to four decimal places (by SAS) it will not be rounded again, but will be presented to four decimal places. P-values less than 0.001 will be presented as “<0.001”, and p-values greater than 0.999 will be presented as “>0.999”.

Confidence intervals (CIs) will be presented to one more decimal place than the raw data.

All report outputs will be produced using SAS® version 9.3 or a later version in a secure and validated environment. The outputs will be provided as individual TLFs in RTF format and all TLFs in one PDF bundle.

All statistical tests will be two-sided and will be performed at the 5% level of significance, unless otherwise stated.

Baseline

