4.4 Analysis Populations

The following analysis populations will be used to analyze the data.

Intent-to-Treat Population (ITT):

The ITT population will consist of all randomized subjects.

Per Protocol Population (PP):

The PP population will comprise all subjects in the ITT population who have no major protocol deviations that would have a significant effect on the efficacy of the study treatment. The PP population will be finalized prior to the final database lock.

Safety Population (SAF):

The safety (SAF) population will comprise all subjects in ITT population who receive at least one dose of study drug.

PK Analysis Population (PKAP):

The PK analysis population will include all subjects in the SAF population who provide at least one post-baseline evaluable drug concentration value.

The efficacy summaries and analyses will be based on the ITT population, which is based upon the Intention-to-Treat (ITT) principle. In the event that a subject is allocated the incorrect study treatment as per the study randomization list, subjects will be summarized and analyzed ‘as randomized’ (i.e., by randomized treatment group). In the event that a subject is stratified incorrectly, ‘randomized stratum’ will be used rather than ‘actual stratum’.

For the primary and selected secondary efficacy endpoints, a sensitivity analysis will be performed on the PP population to assess the robustness of the study conclusions to the choice of analysis population. Subjects will be included in the analysis according to the treatment ‘as randomized’.

The safety summaries and analyses will be based on the SAF population. Randomized subjects will only be excluded if there is clear, documented evidence that the subject did not receive any study drug injection. In the event that a subject is allocated the incorrect study treatment as per the study randomization list, subjects will be summarized and analyzed ‘as treated’ (i.e., by allocated treatment group).

Upon database release, protocol deviation and analysis population outputs will be produced and will be reviewed by Sponsor. An analysis population classification meeting will be arranged to discuss the outputs and to decide which subjects and/or subject data will be excluded from certain analyses. Decisions made regarding the exclusion of subjects and/or subject data from analyses will be made prior to database lock and unblinding and will be documented and approved by Sponsor.

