3. **Worst Observation Carried Forward (WOCF):** The worst observed post-baseline value will be used to replace missing values for continuous variables. For questionnaire-based variables, WOCF will be applied to missing individual questions first, and the value of the total (or sub-scale) score will be derived based on the imputed individual questions.
4. **Observed Case (OC):** No data will be imputed. The observed values are used in analysis, including assessments post rescue medication.
5. **Pattern-mixture model under assumption missing not at random (MNAR), controlled-based pattern imputation:** refer to the 3 phases for MI-based imputation above. With controlled-based pattern imputation, only observations in placebo treatment group are used to derive the imputation model.

Binary endpoints:

All missing values will be treated as a Non-Responder for the binary endpoints. If a subject withdraws from the study, all assessment after withdrawal will be considered as Non-Responder.

LOCF, OC, MI and Pattern-Mixture Model under missing not at random assumption approaches will be used as sensitivity analysis to impute the missing values for the selected secondary endpoints as appropriate. For sensitivity analyses, binary endpoints will be analysed using **Cochran-Mantel-Haenszel (CMH)** test stratified by baseline IGA severity.

There will be no imputations for missing laboratory and vital sign data.

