4.7.3 Secondary Efficacy Endpoints

For analyses up to week 24 using the MMRM approach for continuous endpoints, only data collected up to week 24 will be included in the model.

4.7.3.1 Proportion of subjects achieving IGA success (defined as IGA 0 [clear] or 1 [almost clear]) at each visit up to week 24

A CMH test stratified by baseline IGA severity (3, 4) will be used to test the difference between each nemolizumab regimen and the placebo for the proportion of subjects achieving certain “success” at a given visit for ITT and PP populations. A 95% CI for the treatment difference will be calculated.

A bar chart and line plots will be produced over time for each treatment group to summarize the data (“responders”).

Sensitivity analysis: Sensitivity analyses will be performed as described in 4.7.1.3.

Subgroup analysis: Subgroup analyses will be investigated as described in 4.7.1.6.

Logistic regression will be used with response status as the dependent variable and treatment group, subgroup factor and interaction between treatment group and subgroup as independent variables. Odds ratios and the respective 95% CIs will be used for all subgroup comparisons. In addition, the p-values for the interaction of the treatment groups and the subgroups will also be provided, wherever appropriate.

4.7.3.2 Proportion of subjects achieving IGA success (defined as IGA 0 [clear] or 1 [almost clear]) and a reduction of at least 2 points at each visit up to week 24

This endpoint will be analyzed as described in section 4.7.3.1.

4.7.3.3 Percent change from baseline in EASI at each visit up to week 24

This endpoint will be analyzed as the primary efficacy endpoint using a MMRM approach for ITT and PP populations.

4.7.3.4 Absolute and percent change from baseline in weekly average of the peak and average pruritus NRS at each visit up to week 24

The following endpoints will be analyzed as the primary efficacy endpoint using a MMRM approach for ITT and PP populations.

- Absolute change from baseline in weekly average of the peak pruritus NRS at each visit up to week 24
- Percent change from baseline in weekly average of the peak pruritus NRS at each visit up to week 24
- Absolute change from baseline in weekly average of the average pruritus NRS at each visit up to week 24
- Percent change from baseline in weekly average of the average pruritus NRS at each visit up to week 24

The plots showing the changes over time within each treatment group will be provided.

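### The DLQI 4-point response is tested in all randomised subjects with missing counted as non-response, so subjects who are by design never given the form are scored as failures

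*SAP*

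**What the plan says.** - **Endpoint and test.** SAP 4.9.3.1: "Proportion of subjects achieving a change in DLQI score of at least 4 points at each visit up to week 24 will be analyzed" with the CMH test of SAP 4.7.3.1. That section compares each dose with placebo, stratified by baseline IGA, and adds: "A 95% CI for the treatment difference will be calculated".
- **Population.** SAP 4.9.3: "Primary study population for all QoL and productivity data analyses will be based on ITT population". SAP 4.4: "The ITT population will consist of all randomized subjects".
- **Missing binary data.** SAP 4.7.1.3: "All missing values will be treated as a Non-Responder for the binary endpoints". It makes no exception for a form that was never due.
- **Who receives the DLQI.** SAP 3.2.6.1: "DLQI will be administered only to the subset of subjects who fluently speak a language in which the questionnaire is presented". Protocol 7.5.1 has the same restriction and makes it "based on availability of validated translations in participating countries". The Protocol synopsis plans about 70 sites in Europe, North America and Asia-Pacific.
- **Continuous DLQI score.** SAP 4.9.3.1 also analyses change from baseline by the MMRM of SAP 4.7.2, which carries the baseline value as a covariate.
- **HADS.** SAP 3.2.6.2 applies the same language restriction, and SAP 4.9.3.2 sends the proportions with a sub-score of 11 or more to the same CMH test.

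**The concern.** Non-responder imputation is meant for values lost through dropout, missed visits or rescue, where absence may say something about treatment. Not having a questionnaire in one's language says nothing about treatment. The documents themselves foresee randomised subjects with no DLQI, yet no DLQI-evaluable set is defined, and nothing separates a form not administered by design from a form that is missing.

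Followed literally, the plan puts those subjects in the denominator of every arm with a response fixed at zero. The reported response rates are then too low, the treatment difference and its confidence interval are pulled towards zero, and the test loses power for a reason unrelated to nemolizumab. The MMRM of the same score has no values for these subjects and omits them, so two analyses in the same subsection describe different people.

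**Working it through.** **The plan's own figures.** The documents give no power, response rate or share of subjects not given the form for the DLQI. The only power statement (SAP 4.10, at least 90%) concerns the dose-response test on EASI. It reproduces: simulating the maximum-contrast test over the listed candidate models, with the 30-point effect reached at 90 mg, gives 92.9% to 98.3%. Nothing below affects it.

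**Inputs.** From the documents: 50 subjects per arm (SAP 4.10) and two-sided 5% tests (SAP 4.2). Assumed: f, the share of each arm never given the form, and the response rates p0 (placebo) and p1 (active) among those given it. Randomisation makes f equal across arms in expectation.

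**Effect on the estimate.** With every unadministered form a non-response, each arm's rate becomes p(1-f), and

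difference = p1(1-f) - p0(1-f) = (1-f)(p1 - p0).

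The risk ratio is unchanged and the odds ratio moves towards 1.

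**Effect on the test.** Write pbar = (p0 + p1)/2. Relative to analysing only subjects given the form (n = 50(1-f) per arm), the test statistic is multiplied by about sqrt[(1-pbar)/(1-pbar(1-f))]. The loss therefore grows with the overall response rate. At f=20%:

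- 20% vs 50%, pbar 0.35: sqrt(0.65/0.72) = 0.95
- 50% vs 80%, pbar 0.65: sqrt(0.35/0.48) = 0.85

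**Power.** Unstratified two-proportion normal approximation: Φ[(difference - 1.96·se0)/se1], with se0 pooled and se1 unpooled.

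Example, 50% vs 80% at f=20%:

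- All ITT: rates 40% and 64%, n=50, se0 = sqrt(0.52×0.48×2/50) = 0.0999, se1 = sqrt[(0.24+0.2304)/50] = 0.0970. Power = Φ[(0.24-0.1958)/0.0970] = 68%.
- Given the form: rates 50% and 80%, n=40, se0 = 0.1067, se1 = 0.1012. Power = Φ[(0.30-0.2090)/0.1012] = 82%.

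| Assumed rates | f | Difference, all ITT | Power, all ITT | Power, given the form | Extra loss (points) |
|---|---|---|---|---|---|
| 20% vs 50% | 0 | 30.0 | 89% | 89% | 0 |
| | 5% | 28.5 | 87% | 88% | 1.0 |
| | 10% | 27.0 | 84% | 86% | 2.1 |
| | 20% | 24.0 | 77% | 82% | 4.5 |
| 50% vs 80% | 0 | 30.0 | 89% | 89% | 0 |
| | 5% | 28.5 | 85% | 88% | 3.3 |
| | 10% | 27.0 | 79% | 86% | 6.8 |
| | 20% | 24.0 | 68% | 82% | 14.0 |

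The last column is the cost of the imputation rule. The fall from 89% is not, because restricting the analysis also loses subjects. Pairs with a smaller difference behave similarly: 40% vs 65% loses 2.5 points at f=5% and 8.6 at f=20%; 60% vs 80% loses 4.6 and 13.5.

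**The case against.** The strongest reply is that non-responder imputation may not reach the DLQI at all. The rule sits in SAP 4.7 under efficacy, the DLQI is in SAP 4.9 among other analyses, and SAP 4.9.3.1 refers to 4.7.3.1 only for the test. For DLQI data handling the SAP points to its Appendix 3, where a form with two or more unanswered items is left unscored, not called a failure. SAP 4.2 says of categorical summaries: "Percentages will be calculated using n as the denominator", with n being the subjects who provide data. For HADS the event (11 or more) is unfavourable, so non-responder has no clear meaning there, which suggests the rule was not drafted with this section in mind.

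This shows real ambiguity, and part of it stands: the SAP never says in 4.9.3 that the rule applies. But none of these places gives another missing-data rule for the CMH test, while the population is stated to be all randomised subjects. If table percentages followed SAP 4.2 and the test followed 4.7.1.3, the two would have different denominators. Either way the denominator has to be stated.

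It also stands that f may be zero, if suitable versions cover everyone enrolled, and that the loss is supportive only: quality of life is in no stated objective.

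A reader might go further and infer that subjects with a baseline DLQI below 4 are also fixed non-responders. The documents do not support that. The criterion in SAP 4.9.3.1 gives no direction, and Appendix 3 counts an increase or a decrease of at least 4 points, so a subject going from 2 to 6 meets it as written. Nor do the documents give a baseline DLQI distribution from which to size such a group.

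**Conclusion.** The point holds for the language subset. Read as written, SAP 3.2.6.1, 4.4, 4.7.1.3 and 4.9.3 together score randomised subjects who were never due a DLQI as treatment failures, and the risk difference shrinks by exactly (1-f). For the two assumed 30-point scenarios the extra power loss is about 1 to 3 points at f=5% and about 5 to 14 points at f=20%. Those figures rest on assumed response rates and an assumed f; at f=0 there is no effect.

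A reader might infer a bias in favour of the drug or a threat to the trial's main conclusion. Neither follows. The dilution is non-differential in expectation, works towards no difference and does not inflate type I error. The primary endpoint, the listed secondary efficacy endpoints and the sample size are untouched. This is a correction worth making before unblinding to a supportive analysis that will report a p-value and a confidence interval.

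**What to change.** In SAP 4.9.3.1:

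- Define the denominator of the DLQI response as ITT subjects with a scored baseline DLQI.
- Apply non-responder imputation only to later missing values in that set.
- Report by arm how many randomised subjects are excluded.
- State that response means a decrease (improvement) of at least 4 points.

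In SAP 4.9.3.2, restrict the HADS CMH analyses in the same way to ITT subjects given the HADS with a scored baseline sub-scale, and do not count a form never given as an outcome in either direction.

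No minimum baseline DLQI is needed. Subjects with low baseline scores remain in the MMRM, and keeping them here holds the two DLQI analyses closer together. Protocol 8.1.2.1 lists the questionnaires ahead of randomisation and dosing at the baseline visit, so membership is fixed before treatment and the randomised comparison is kept.

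The cost is a few sentences in the SAP and one programming flag per instrument. The downside is a smaller denominator that is no longer all randomised subjects, which the table should say.
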